5. The patient has given signed informed consent.
6. TAVI performed via the femoral artery.

Centers eligible for inclusion: Scandinavian and European centers who fulfill the above mentioned criteria.

Randomization:

Before randomizing patients, the center decides which two valves the patient is found eligible for, and enters these valves in the electronic randomization form (TrialPartner). Randomization is then performed between these two valves. A patient is only randomized if a dedicated technical TAVI conference has found the patient eligible for treatment with both valves.

Consecutive cohorts are established.

We plan to initiate the following cohorts:

Cohort A: Patients randomized to the Sapien or the Accurate neo 2 TAVI valve (Approved, not recruiting, await funding).

Cohort B: Patients randomized to the Sapien or the Myval TAVI valve (Recruiting).

Cohort C: Patients randomized to a BEV valve (To be determined whether Sapien or Myval) compared to the Navitor valve (Awaits approval and funding).

Operator requirements:

Any procedure requires that the physician has performed at least 15 implantations with the valve in use. Otherwise the procedure is performed according to the routine of the institution.

Primary endpoints, for each cohort:

1. MACE: Mortality, stroke, moderate/major PVL, moderate/severe valve deterioration at 1 year, using VARC-3 criteria (10).

Secondary endpoints, for each cohort:

1. MACE: Mortality, stroke, moderate/major PVL, moderate/severe valve deterioration at 30-day, 3-year, 5-year and 10-year, using VARC-3 criteria (10).
2. Mortality: 30-day, 1-year, 3-year, 5-year and 10-year.
3. Stroke: During admission, 30-day, 1-year, 3-year, 5-year and 10-year, using VARC-3 criteria (10).
4. Moderate or severe PVL: 30-day, 1-year, 3-year, 5-year and 10-year, using VARC-3 criteria (10).
5. Moderate or major valve deterioration: 30-day, 1-year, 3-year, 5-year and 10-year, using VARC-3 criteria (10).
6. Pacemaker-implantation: during admission, 30-day, 1-year, 3-year, 5-year and 10-year.
7. Major bleeding resulting in drop in hgb-level ≥ 1.86 mmol/l and/or erythrocyte transfusion ≥ 2 units: during admission, 30-day, 1-year, 3-year, 5-year and 10-year, modified from BARC type 3-5 criteria (11, 12).
8. 6-minute walk test: baseline, 30-day, 1-year, 3-year, 5-year and 10-year.

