25. CABG (not scheduled before TAVI), 30-day, 1-year, 3-year, 5-year and 10-year according to VARC-3 criteria (10).
26. Reoperation (TAVR, SAVR, BAV), 30-day, 1-year, 3-year, 5-year and 10-year according to VARC-3 criteria (10).
27. Newly diagnosed atrial fibrillation/flutter, 30-day, 1-year, 3-year, 5-year and 10-year according to VARC-3 criteria (10).

Registration of endpoints:

The majority of endpoints are collected from national registries. An echo core-lab is established to evaluate echo parameters (degree of PVL moderate/severe, valve deterioration, thrombosis). A CT core-lab is established to evaluate CT parameters (leaflet thickening, reduced leaflet motion, leaflet thrombosis, coronary alignment). An MRI core lab is established to evaluate MRI parameters (EOA and volume of aortic regurgitation). A separate core lab is established for analysis of aortaograms (videodensitometry) following TAVI. Procedure-related complications are manually collected from electronic patient files. At each follow-up (1-month, 1-year, 3-year, 5-year, 10-year) each site also monitor events and file them in the ECRF, thus both site-reporting and registry-validation of events. Selected endpoints are adjudicated by an endpoint committee (Stroke, AMI, readmission with heart failure, endocarditis).

Power calculations:

For each cohort (randomized comparison between two valves) the steering committee decides to perform the study with or without interim analyses. In case interim analyses is chosen, a safety committee will compare outcome after inclusion of approximately 1/3 and 2/3 of patients (interim analyses). If one valve is

not clearly inferior, randomization will continue until the complete cohort is included. The size of the cohort is dependent of expected event-rate, chosen non-inferiority margin, number of interim analyses and expected drop-out. See table below. With 2 interim analyses and a non-inferiority margin of 4%, event rate 9% and expected drop out of 5% the sample size should be 1346 patients. If including 1062 patients as planned in cohort B, and with no interim analyses and 5% drop-out, the non-inferiority margin would be 4% if the event-rate is 7% and 4.5% if the event rate is 9%. If the observed event-rate differ significantly from the expected, the steering committee should consider adjusting sample size or non-inferiority margin (see table below).

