For each cohort the maximal inclusion period is 3 years, and the first interim analysis (if planned according to the steering committee) will be performed after no later than two years of inclusion. A cohort will also be closed for inclusion, if one of the study valves is retracted from the market or replaced by a new generation of the device.

Number of centers and procedures per center: The prerequisite for initiating a comparison between two valves is that at least 3 centers will randomize from the beginning, that at least 10 centers are expected to randomize in each cohort, and that each center aims at including at least 50 patients per year.

Statistics: Data will be analyzed according to the intention-to-treat principle. Continuous data will be presented as mean \pm SD, and compared using a t-test, if data are normally distributed. If data are not normally distributed the Mann Whitney U test will be used. Categorical variables will be compared using Fischers exact test or Chi-square test as appropriate, and data presented as numbers and percentages. Significance level is $p<0.05$ (double sided). When comparing primary endpoints, a non-inferiority analysis will be used. When comparing secondary endpoints, Cox regression and logistic regression analyses will be used, as appropriate. Kaplan-Meir curves will be used for graphical presentation of time to events.

Data management: Data will be collected and stored according to the Danish data protection legislation. TrialPartner will be used for the Electronic Case Report form (ECRF). Patient and procedural characteristics will be entered in the ECRF following the procedure and at time of discharge. Follow-up (30-day, 1-year, 3-year, 5-year and 10-year) will be conducted mainly registry based (CPR-registry, National patient registry, Invasive registry), but at each follow-up the site will also check for events, and file them in the ECRF. This will ensure two sources for event-registration. Regarding moderate and severe PVL, moderate and severe aortic stenosis, and presence of thrombus or leaflet thickening, data will be entered by the Echo and HCT core labs. MRI findings will be entered by the MRI core lab. TrialPartner is approved by the Danish data regulative, and data entry and access will be logged. When a cohort is terminated, data will be merged and anonymized and a key stored with the CPR-number.

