Biobank: No biobank is collected.

Blinding: The study is not blinded.

Data from patient records: As part of the study data on previous disease (hypertension, diabetes, stroke, myocardial infarction, congestive heart failure), age, sex, Echocardiographic findings, HCT-findings will be collected from the patient records. These data will only be used for study purposes, and will be anonymized when the study is terminated. In situations where these data cannot be collected from registries, they will be retrieved from patient records. The purpose is to use these data in anonymous form when publishing the final results.

Data management and approvals: The Danish Data protection legislation will be followed. The study will be filed to the Danish Data protection agency and the local Ethical committee, and filed to www.clinicaltrial.gov before inclusion starts. In Denmark the national board of health will applied for data from the CPR-registry and the national patient registry. Data can be shared in anonymous form for research purposes.

Access to data: Data is stored in TrialPartner. All data is encrypted. Any access or attempt to access data will be logged. Investigator/Institution will allow monitoring or audit from the ethical committee or the data protection agency as well as the national board of health who will be given access to source data and patient records. Investigator is responsible for ensuring that any patient has been given written consent to access source data (patient record).

Safety committee:

A separate safety committee is established for each cohort. The members are physicians not implanting TAVI-valves.

Event committee:

A separate event committee is established to adjudicate selected endpoints (Stroke, AMI, endocarditis, readmission with CHF).

Steering committee:

For each cohort a steering committee is established with one representative from each of the centers randomizing patients in this cohort. The chair is the physician who from the beginning is responsible for this cohort.

Coordinating center:

The research department at Aarhus University Hospital will be the coordinating center, and responsible for establishing a digital CRF for the trial, and responsible for collecting data, monitoring, coordinating safety committee, event committee and steering committee meetings and publications.

Economy/Funding:

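### Nothing in the plan masks the event committee or the echo core lab, so three of the four primary components can be graded with the valve known

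*Combined protocol and SAP*

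**What the plan says.** The Blinding section is a single sentence, "The study is not blinded", with no exception for those who assess outcomes.

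The primary endpoint for each cohort is "MACE: Mortality, stroke, moderate/major PVL, moderate/severe valve deterioration at 1 year, using VARC-3 criteria (10".

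Responsibility for the components that need judgement is set out under Registration of endpoints and Event committee:

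- Stroke: "Selected endpoints are adjudicated by an endpoint committee (Stroke, AMI, readmission with heart failure, endocarditis". The Event committee section repeats the same list of events.
- PVL and valve deterioration: "An echo core-lab is established to evaluate echo parameters (degree of PVL moderate/severe, valve deterioration, thrombosis".
- Reporting by sites: at each follow-up, "each site also monitor events and file them in the ECRF, thus both site-reporting and registry-validation of events".

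The Data management section adds that "When a cohort is terminated, data will be merged and anonymized and a key stored with the CPR-number". The Safety committee section requires members who do not implant these valves. No such condition is stated for the event committee or the core labs.

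**The concern.** Implanting physicians cannot be blinded to the valve they deploy, so an open-label procedure is not itself the problem. Those who classify outcomes afterwards can be masked, at least in part, and the plan does not ask for it. Stroke has to be adjudicated, and PVL and deterioration count only from a severity threshold upwards. Borderline cases are where knowledge of the valve could influence a grade.

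The primary analysis is a non-inferiority comparison on the absolute difference in event proportions. A small net shift in grading in one arm moves that difference directly. A shift in favour of the test valve makes a false claim of non-inferiority more likely. A shift against it makes a true claim harder to establish.

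**Working it through.** **1. Is any assessor masked?** Setting the relevant sections side by side:

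| Primary component | Who determines it | Masking stated? |
|---|---|---|
| Mortality | Registries, with site reports | Not stated; little room for judgement |
| Stroke | Event committee | No |
| Moderate/major PVL | Echo core lab | No |
| Moderate/severe valve deterioration | Echo core lab | No |

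The provisions that come closest do something else. Anonymization happens when a cohort is terminated and serves data protection. The condition on members' practice applies to the safety committee only. Registry cross-checking improves event capture, but sites that know the valve also file events. VARC-3 supplies definitions; it does not hide the allocation.

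**2. Reproduce the plan's sample size, to fix the alpha level.** The table under Power calculations gives power 0.80 and alpha 0.05. The total is 2 × n per arm, with

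n per arm = (z₁₋α + z₀.₈₀)² × 2p(1−p) / margin²

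- 7% rate, 4-point margin, one-sided 0.05: (1.645 + 0.842)² × 2 × 0.07 × 0.93 / 0.04² gives 504 per arm, total 1008. Dividing by 0.95 gives 1062. Both match the table.
- 9% rate, 4.5-point margin, one-sided 0.05: total 1002, also a match.
- One-sided 0.025 would need 1278 and 1270, which do not match.

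The table therefore rests on one-sided 0.05, although the Statistics section gives a double-sided 0.05 level.

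**3. Hypothetical effect of a grading shift b.** Inputs from the plan: 1062 patients with 5% drop-out leaves 1009 evaluable, or 504.5 per arm; reference rate 9%; margin 4.5 points. The values of b are assumptions. A shift of 0.5 point is 0.005 × 504.5 ≈ 2.5 patients, and 1.0 point is about 5 patients.

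*False non-inferiority.* The true difference equals the margin, and the observed test-valve rate is 13.5% − b:

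P = Φ(b/SE − 1.645), SE = √[(0.09 × 0.91 + p_T(1 − p_T)) / 504.5]

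- b = 0: 5%.
- b = 0.005: p_T = 0.130, SE = 0.01966, P = Φ(−1.391) = 8.2%.
- b = 0.010: p_T = 0.125, SE = 0.01947, P = Φ(−1.131) = 12.9%.

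*Loss of power.* The valves are truly equal, the shift goes against the test valve, and SE is held at its planning value √(2 × 0.0819 / 504.5) = 0.01802:

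Power = Φ((0.045 − b)/0.01802 − 1.645)

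- b = 0: 80%.
- b = 0.005: 71.7%.
- b = 0.010: 61.7%.

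Recomputing SE at the shifted rate gives 71% and 60% for the last two.

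**4. Sensitivity.**

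- At a 7% rate and 4-point margin (one-sided 0.05), false non-inferiority becomes 8.6% or 14.1%, and power 69% or 57% (SE recomputed).
- At 9% and 4.5 points with z = 1.96, false non-inferiority goes from 2.5% to 4.4% or 7.4%.

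**The case against.** The strongest reply is that the sentence on blinding can be read as describing patients and operators only, and that silence about assessors is not a rule that they work unmasked. This stands in part. A reader might infer that the committee and core lab did grade with the valve known. The documents do not support that: they leave it open, and a charter not included here may require masking.

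The plan also limits discretion in other ways. Events are recorded from two sources, echo findings are entered by a core lab and not by sites, and VARC-3 criteria apply. These are real protections, but none keeps the allocation from the assessor.

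On size, nothing in the documents suggests that a shift of 0.5 or 1.0 point is likely. At a 13.5% test-valve rate the arm would have about 68 events (0.135 × 504.5). Some would be deaths, which cannot be regraded, so a full point needs about 5 net misgradings in one direction among the rest. The calculation shows sensitivity and is not an estimate of bias.

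A reader might also infer that manufacturer funding makes biased grading likely. The Economy/Funding section says the companies have no influence on design or conduct, and cohort B also had heart-foundation support. No link from funding to grading is shown, and the point does not rely on one.

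Finally, the valve may be recognisable on echo, so masking there may be only partial. That is a reason to record where it failed. It does not apply in the same way to stroke files, where the valve name can be removed.

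**Conclusion.** The point holds in a limited form. The plan's one statement on blinding permits unmasked grading of stroke, PVL and valve deterioration, and nothing elsewhere in the documents restricts it. Mortality is little affected. This does not establish that any assessor was unmasked or that any result is biased.

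The figures in the working are hypothetical. They rest on an assumed net shift, on one-sided 0.05 and on the cohort B planning values. Their use is to show that a net 2 to 5 patients graded differently in one arm is enough to change the error rates noticeably. The plan should be amended, because the safeguard is inexpensive and bears on the primary endpoint.

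**What to change.** Amend the Blinding section to state that:

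- patients, operators and sites are not blinded;
- the event committee receives case files with valve name and allocation removed;
- echo core-lab readers receive coded studies without allocation or site reports, and record each study in which the valve is recognisable on the image.

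If a charter already requires this, the protocol should say so. If masking is not feasible for a component, the protocol should give the reason. CT and MRI readers can be treated the same way, but this is optional because their findings are secondary or sub-study measures.

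The cost is the protocol wording plus redaction and coding by the coordinating center, which already coordinates the event committee. Sample size, endpoints and planned assessments do not change. Two limits remain: masking on echo may be incomplete, and masking assessors does not remove the sites' knowledge of the valve when they report events.
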